6.2. Analysis of Primary Endpoint

6.2.1. Primary Analysis

Part A

The primary analysis will be performed on MITT subjects with a baseline and at least one post-baseline joint count assessment. For joint count assessments, the analyses will be conducted using pooled subjects' data from PV2 and PV1 who meet the criteria as described in [Section 3.1](#).

The continuous primary endpoint, change from baseline to week 24 in the active joint count, will be analyzed as described for continuous endpoint analysis in [Section 6.1.1](#)

Part B

The primary analysis will be performed on MITT subjects with a baseline and at least one post-baseline CLASI-A assessment. The analyses will be conducted using pooled subjects' data from PV2 and PV1 who meet the criteria as described in [Section 3.1](#).

The primary analysis of the primary endpoint, percent change from baseline to week 16 in CLASI-A score, is a test of dose-response, using the Multiple Comparison Procedure – Modelling (MCP-Mod) methodology [\[Bretz 2005\]](#).

Five dose-response trends will be tested using the appropriate contrasts, as determined by the MCP-Mod methodology, on the treatment effects obtained from the MMRM model.

The MMRM model will be applied to percent change from baseline in CLASI-A score as described for endpoint analysis in [Section 6.1.2](#)

For MCP-Mod Candidate Models, two families of dose-response models (or 'candidate models') will be considered:

- SigEmax models (4 candidates) - parameters to estimate: e0, emax, h and ED50

$$\text{SigEmax} - \mu d = e0 + emax * d^h / (ED50^h + d^h),$$

CONFIDENTIAL

The information contained herein may not be used, disclosed, or published without the written consent of Biogen MA Inc.

where: $emax$ = asymptotic maximum effect; $ED50$ = Dose giving half of the asymptotic maximum effect; $e0$ = placebo effect and h = shape parameter.

- Beta model (non-monotonic, 1 candidate)

$$\text{Beta model} - \mu d = e0 + emax B(\delta 1, \delta 2) x^{\delta 1} (1-x)^{\delta 2}$$

where: $emax$ = asymptotic maximum effect; $e0$ = placebo effect;

$$B(\delta 1, \delta 2) = (\delta 1 + \delta 2)^{(\delta 1 + \delta 2)} / (\delta 1^{\delta 1} \delta 2^{\delta 2}); x = d/\text{scale}$$

The initial parameters for candidate models are as follows:

- SigEmax model 1: ($ED50 = 25$, $h = 2.5$)
- SigEmax model 2: ($ED50 = 50$, $h = 2.1$)
- SigEmax model 3: ($ED50 = 90$, $h = 2.5$)
- SigEmax model 4: ($ED50 = 450$, $h = 1$)
- Beta Model: ($\text{scale} = 720$) ($\delta 1 = 0.6425$, $\delta 2 = 1.235$)

The maximum treatment effect (over placebo within the dose range) is assumed to be 27.5 at week 16. The four candidate SigEmax models were considered in order to capture different $ED50$ values (ranging from 25 to 450 mg). The beta model was considered to capture the scenario where maximum benefit is not observed at the highest but is observed at a lower dose.

[figure not shown]
[figure not shown]
If at least one model is significant, there is an indication for evidence of a dose-response effect. A candidate model will be selected using model selection criteria AIC (Akaike Information Criteria). The selected model will be used to produce estimates of target doses using modeling and simulations.

To further understand the dose-response relationship, based on the model type (sigmoid Emax model or Beta model) selected from the MCP-Mod method, a sigmoid Emax model or Beta model will be fitted using data from week 16. For subjects who are missing with week 16 visit data, the predicted value from the MMRM model will be used to fit the dose-response model.

CONFIDENTIAL

The information contained herein may not be used, disclosed, or published without the written consent of Biogen MA Inc.

The dose-response model parameters, such as Emax and ED50, will be estimated as well as the treatment effect of each dose group.

CONFIDENTIAL

The information contained herein may not be used, disclosed, or published without the written consent of Biogen MA Inc.

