16.1. Efficacy

16.1.1. Analysis Population

For Part A and Part B, analysis of efficacy endpoints will be based on the intent-to-treat (ITT) population and the per-protocol (PP) population.

The ITT population is defined as all randomized subjects who received at least 1 dose of study treatment (whether or not the subjects adhered to the protocol). Subjects will be analyzed according to the study treatment to which they were randomized. Analysis of other non-safety endpoints (e.g., demographics) will also be based on the ITT population, unless otherwise specified in the SAP.

The PP population is defined as all subjects in the ITT population who do not meet the criteria for exclusion from analysis. The exclusion criteria will be defined prior to database lock for the final analysis.

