4.1. Definitions of Analysis Populations for Part A and Part B

Modified Intent-to-Treat (MITT) Population

The MITT population is defined as all randomized subjects who received at least 1 dose of study treatment (whether the subjects adhered to the protocol). Subjects will be analyzed according to the study treatment to which they were randomized. Analysis of other non-safety endpoints (e.g., demographics) will also be based on the MITT population.

Safety Population

The safety population will include the same subjects as defined for the MITT population. However, subjects will be analyzed by actual treatment received. If all subjects take the treatment as they were randomly assigned to, the safety population will be the same as the MITT population.

Per-Protocol (PP) Population

The per-protocol population will include the MITT subjects who do not have any major protocol deviations that could impact the efficacy assessments. Subjects will be analyzed by randomized treatment. Major deviations that could impact the efficacy assessments are:

Part A

- Actual treatment received is different from the planned treatment (e.g., patients received BIIB059 treatment while randomized to the placebo arm).
- Patients who have usage of disallowed concomitant therapy or SLE standard of care therapy that deviate from the protocol (specific rules for each concomitant therapy will be described in an addendum).
- Failing Inclusion/exclusion criteria that might potentially affect efficacy. The criteria listed in [Table 1](#) are considered not going to affect efficacy, thus they are not considered for per-protocol population.
- < 80% treatment compliance with study medication

CONFIDENTIAL

The information contained herein may not be used, disclosed, or published without the written consent of Biogen MA Inc.

- > 120% treatment compliance with study medication

Part B

- Actual treatment received is different from the planned treatment (e.g., patients received BIIB059 treatment while randomized to the placebo arm).
- Patients who have usage of disallowed concomitant therapy or SLE standard of care therapy that deviate from the protocol (specific rules for each concomitant therapy will be described in an addendum).
- Failing Inclusion/exclusion criteria that might potentially affect efficacy. The criteria listed in Table 1 are considered not going to affect efficacy, thus they are not considered for per-protocol population.

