6. EFFICACY ANALYSES

6.1. General Considerations

For both Part A and Part B, the efficacy analyses will be performed using the MITT population and will be considered as the primary analyses. For each endpoint, additional conditions may apply for pooling of data across protocol versions (see [Section 3.1](#)). The final model for each analysis in the MITT population will also be used for the PP analysis. A complete list of all the planned analyses and target population for the primary and secondary endpoints is provided in [Appendix A1](#) (Part A) and [Appendix A2](#) (Part B).

Unless otherwise specified, statistical testing across all efficacy endpoint will be performed to compare each BIIB059 dose (Part A: 450 mg; Part B: 50, 150 or 450 mg) with placebo at the 2-sided, 0.05 significance level. P-values and corresponding 95% confidence intervals (CI) will be provided. P-values will be rounded to three decimal points before assessing statistical significance.

CONFIDENTIAL

The information contained herein may not be used, disclosed, or published without the written consent of Biogen MA Inc.

 Biogen	Statistical Analysis Plan 230LE201	<V 2.0>
--	---	----------------------

Summary statistics will be presented for all endpoints at all visits including follow-up visits. For continuous variables, the summary statistics will include number of subjects with data, mean, standard deviation (SD), median, first quartile (Q1), third quartile (Q3), minimum and maximum. For categorical endpoints, the summary statistics will generally include: number of subjects in the corresponding analysis population, number and percentage of subjects in each category.

Unless otherwise specified, week 2, 4, 8, 12, 16, 20 and, 24 will be included in all Part A “by visit” MMRM analyses.

Unless otherwise specified, week 2, 4, 8, 12 and, 16 will included in all Part B “by visit” MMRM analyses.

Additional study part specific efficacy analyses considerations are described in [Section 6.1.1](#) (Part A) and [Section 6.1.2](#) (Part B)

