6.2.2. Sensitivity Analysis

A sensitivity analysis will be performed on both part A and part B primary endpoints using the same methods as described in [Section 6.2.1](#) but using a different missing data handling approach, reference based multiple imputation, as described in [Section 6.6](#).

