6.6.1. Continuous Endpoints

The primary approach described below will apply to both part A and part B continuous endpoints, unless otherwise specified. The sensitivity approach will be applied to the primary endpoints.

Primary approach

For subjects who are considered as treatment failures, as defined in [Section 5.8](#), the worse observation of the baseline and the last observation before treatment failure carried forward will be used as the primary method to impute values for all the visits post treatment failure visit. Under this approach, subject's post treatment failure data will be censored and then imputed with the subject's worst case non-missing data prior to treatment failure.

Data after treatment discontinuation will be censored and treated as missing data. For all other monotone and non-monotone missing data, including missingness post treatment discontinuation, mixed-effects model repeated measures (MMRM) model based approach will be used as the primary approach. MMRM assumes data is missing at random (MAR).

A few subjects from PV1 part B might have completed treatment up to week 12 but could not reconsent to PV2 and therefore will have missing week 16 data. These subjects will have week 16 data imputed using predicted value from the MMRM model.

Sensitivity analyses approach

For subjects who are considered as treatment failures, as defined in [Section 5.8](#), the worse observation of the baseline and the last observation before treatment failure carried forward will be used to impute values for all the visits post treatment failure visit. Under this approach, subject's post treatment failure data will be censored and then imputed with the subject's worse case between the baseline and the last non-missing data prior to treatment failure.

CONFIDENTIAL

The information contained herein may not be used, disclosed, or published without the written consent of Biogen MA Inc.

 Biogen	Statistical Analysis Plan 230LE201	<V 2.0>
--	---	----------------------

For all the other missing data, including missingness post treatment discontinuation, reference-based Multiple Imputation (MI) approach will be used to consider a missing not at random (MNAR) mechanism for monotonic missing data. Imputed values of subjects in the BIIB059 group will be based on the Placebo group. This approach assumes no sustained benefit of BIIB059 after discontinuation of study treatment and limits post-discontinuation effects to that of placebo.

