6.6.2. Binary Endpoints

The non-responder imputation (NRI) approach will apply to both part A and part B binary endpoints, unless otherwise specified.

Subjects who are considered as treatment failures, as defined in [Section 5.8](#), will be considered as non-responders for all the visits post treatment failure visit.

Subjects who discontinued treatment will be classified as non-responders for all the visits following treatment discontinuation. Intermittent (non-monotonic) missing data will be imputed based on last observation carried forward (LOCF) approach. Subjects who completed treatment but had a missing score at primary timepoint (Week 24 of Part A or Week 12, 16 of Part B) will also be classified as non-responder for that timepoint, except for subjects from PV1 Part B who completed treatment up to week 12. These subjects will have the binary response derived based on the imputation of week 16 data under MAR assumption as discussed in [Section 6.6.1](#).

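### The post-baseline requirement in SAP 6.2.1 removes treatment failures that SAP 6.6.1 can score from baseline, and leaves it unclear whether the sensitivity analysis includes subjects with only a baseline

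*SAP*

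**What the plan says.** The base population requires no post-baseline score. Protocol 16.1.1: "The ITT population is defined as all randomized subjects who received at least 1 dose of study treatment". SAP 4.1 renames the population but keeps the content: "The MITT population is defined as all randomized subjects who received at least 1 dose of study treatment". SAP 6.1 adds that "the efficacy analyses will be performed using the MITT population and will be considered as the primary analyses".

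SAP 6.2.1 then narrows the set for both primary endpoints. Part A: "The primary analysis will be performed on MITT subjects with a baseline and at least one post-baseline joint count assessment". Part B: "The primary analysis will be performed on MITT subjects with a baseline and at least one post-baseline CLASI-A assessment".

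Three other rules bear on the subjects this removes.

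- **Failure rule (SAP 6.6.1).** After a treatment failure, all later visits are filled with "the worse observation of the baseline and the last observation before treatment failure carried forward". The primary and sensitivity approaches share this rule.
- **Sensitivity analysis (SAP 6.2.2).** "A sensitivity analysis will be performed on both part A and part B primary endpoints using the same methods as described in" 6.2.1, with only the missing-data handling changed, to reference-based multiple imputation. SAP 6.6.1 imputes monotone gaps for everyone who stops treatment early, from a placebo-only model that contains baseline score and stratification factors.
- **Responder endpoints (SAP 6.6.2).** "Subjects who discontinued treatment will be classified as non-responders for all the visits following treatment discontinuation". Failures are treated the same way, and SAP 6.3.1 to 6.3.3 state no post-baseline condition.

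**The concern.** Requiring a post-baseline score is common and costs a plain MMRM nothing. Here it sits beside a rule that deliberately assigns an outcome to failures. Because that rule includes baseline, a subject who fails before the first score has a defined outcome: no change. SAP 6.2.1 removes the subject before the rule can act.

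The sensitivity analysis has a related problem. Its stated assumption is that benefit does not persist after stopping BIIB059, and the earliest dropouts are the plainest case. Two programmers could follow different sentences of the SAP and obtain different numbers of subjects.

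What is at stake is an unambiguous primary set before unblinding, a failure rule that covers every failure, and, in Part B, percent change in CLASI-A and CLASI-50 referring to the same randomised subjects.

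**Working it through.** **1. The plan's own figures.**

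- Part A (Protocol 16.8): 50 per arm less 20% gives 40; SD 6, difference 2.5, two-sided 0.2. Standard error 6 × √(2/40) = 1.34. Power is 71.7% (stated 71%). With 85 less 20% = 68 per arm it is 87.3% (stated 87%). SAP Section 11 prints 0.02 as the significance level, which gives 32%; that is a separate matter.
- Part B: 25 less 20% gives 20 per arm; SD 30, maximum effect 27.5, five candidate models, one-sided 0.05. Simulated MCP-Mod power is 89% to 94% by shape, mean 92% (stated about 90%).

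The inputs are sound, but they do not settle who is analysed.

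**2. Two failures with the same usable data.** Suppose two Part B subjects start a disallowed therapy on Day 10, before any post-baseline CLASI.

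- The first returns once, at Week 4. SAP 6.6.1 censors that score and fills in baseline. The subject appears to meet the 6.2.1 condition and enters as 0% change.
- The second leaves with no further score. SAP 6.6.1 would also give 0% change, but 6.2.1 excludes the subject.

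Inclusion turns on a score that the plan then discards. SAP 6.2.1 does not say whether a censored score counts. The retrieved-dropout analysis in SAP 6.10 does not restore the second subject, because it uses only scores that were collected.

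**3. How many leave before a first score.** The documents give no count. Assume the planned 20% dropout at a constant hazard over T weeks and no early termination (ET) score. The share gone by week t is 1 − 0.8^(t/T).

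The first Part B CLASI is uncertain. In the text available, the CLASI row of Protocol Table 2 appears to carry a mark at Week 1. SAP 4.3 and 6.1.2 list Week 2. The Version 2 amendment summary says Week 2 was removed, which would leave Week 4. All three are shown. For Part A, Protocol Table 1 has the first joint count at Week 2.

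| Part, first score | Share | Per arm | Shrinkage if imputed as placebo |
|---|---|---|---|
| B, Week 1 | 1 − 0.8^(1/16) = 1.4% | 0.3 of 25 | 0.014 × 27.5 = 0.4 points |
| B, Week 2 | 1 − 0.8^(2/16) = 2.8% | 0.7 of 25 | 0.0275 × 27.5 = 0.8 points |
| B, Week 4 | 1 − 0.8^(4/16) = 5.4% | 1.4 of 25 | 0.054 × 27.5 = 1.5 points |
| A, Week 2 | 1 − 0.8^(2/24) = 1.8% | 0.9 of 50 | 0.018 × 2.5 = 0.05 joints |

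The last column follows because giving a share f of an active arm the placebo mean turns the effect into effect × (1 − f). One Part B subject in 25 gives 27.5 × 24/25 = 26.4.

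**4. Direction under the failure rule.** Take 25 per arm, a placebo improvement p (assumed 0 to 30%) and an active improvement of p + 27.5. One subject is scored 0% instead of excluded.

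- In the active arm: (p + 27.5) × 24/25 − p = 26.4 − p/25, which is 26.4 to 25.2. The difference shrinks.
- In the placebo arm: (p + 27.5) − p × 24/25 = 27.5 + p/25, which is 27.5 to 28.7. The difference stays the same or grows.

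**5. Scale.** The planned Part B pairwise standard error is 30 × √(2/20) = 9.5, so 1.5 points is about 0.16 of it. In Part A, 0.05/1.34 is about 0.04.

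**The case against.** The strongest reply is that the affected group is close to empty. An excluded failure must fail before the first score, leave, and miss the ET visit. The protocol works against each step: failures may stay on study (11.4.1.1.1, 11.4.1.1.2.3), and subjects who stop are asked for ET assessments within 4 weeks (7.2.3, 7.3.3). SAP 4.3 windows ET and unscheduled scores from Day 2, so one such score meets the condition. In Part A an allowed Rescue 1 in Weeks 1 to 4 is not a failure (SAP 5.8). This stands, and it limits the size. It does not remove the inconsistency, because an ET visit can be declined.

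The restriction also fits the protocol's failure rule (16.1.2.1), which carries forward the last post-baseline value and gives no score to a subject with only a baseline. That is correct. The conflict lies within the SAP, whose rule brings baseline in.

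Four stronger readings are tempting, and the documents do not support them.

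- **The sensitivity analysis excludes the earliest dropouts.** SAP 6.2.2 carries over methods without naming a set. SAP 6.6.1 speaks of all who stop treatment early, and its model could impute them. The lists of target populations (Appendix A1 and A2) are not readable.
- **The exclusion flatters BIIB059.** Step 4 shows that the failure rule can move the difference either way.
- **About 5% of Part B is lost.** That takes the latest possible first CLASI and assumes no ET scores.
- **The same subjects are non-responders in every responder analysis.** In Part A, SAP 3.1 admits subjects from protocol version 2 onward to CLASI endpoints only if baseline CLASI-A is at least 8.

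**Conclusion.** The concern holds in a limited form. Read as written, SAP 6.2.1 excludes treatment failures with no post-baseline score, although SAP 6.6.1 can score them as no change. No readable passage restores them. For the sensitivity analysis the SAP is ambiguous about subjects with only a baseline; exclusion is not established. For ordinary dropouts the primary MMRM is unaffected.

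The likely effect is small: at most about 1.5 CLASI-A percentage points and 0.05 joints in the sensitivity estimate, and an effect of either sign from early failures. These sizes rest on constant-hazard dropout of 20%, no ET scores and arms of 25 and 50. Pooling version 1 subjects enlarges the Part B 450 mg and placebo arms, so shifts per subject there would be smaller. The planned Phase 2 conclusion is unlikely to turn on this. It is a cheap improvement.

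**What to change.** In SAP 6.2.1, define the primary set for each part as all MITT subjects with a baseline value who meet the Section 3.1 pooling criteria. Add that a treatment failure without a post-baseline value is scored as no change from the failure onward. This also makes it irrelevant whether a censored score counts.

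In SAP 6.2.2, state that the reference-based imputation includes every such subject, including those with no post-baseline score. Align Appendix A1 and A2 if they say otherwise.

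The cost is a short edit to each of the two sections, made before unblinding, with no new data. The one drawback is that the sensitivity estimate may become slightly less favourable.

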6.2.2. Sensitivity Analysis

A sensitivity analysis will be performed on both part A and part B primary endpoints using the same methods as described in [Section 6.2.1](#) but using a different missing data handling approach, reference based multiple imputation, as described in [Section 6.6](#).

6.3. Analysis of Secondary Efficacy Endpoints

6.3.1. CLASI-50 Response (Yes/No)

Part A

The percent reduction from baseline to Week 24 in the CLASI-A score will be calculated for each subject. The proportion of subjects who had CLASI-50 response, defined as a $\geq 50\%$ reduction in the CLASI-A score from baseline, will be analyzed as described for binary endpoint analysis in [Section 6.1.1](#)

Part B

The percent reduction from baseline to Week 12 and 16 in the CLASI-A score will be calculated for each subject. The proportion of subjects who had CLASI-50 Response at week 12 and 16, defined as a $\geq 50\%$ reduction in the CLASI-A score from baseline, will be analyzed separately for each time point as described for binary endpoint analysis in [Section 6.1.2](#).

CONFIDENTIAL

The information contained herein may not be used, disclosed, or published without the written consent of Biogen MA Inc.

 Biogen	Statistical Analysis Plan 230LE201	<V 2.0>
--	---	----------------------

6.3.2. A 4-Point Reduction in CLASI-A Response (yes/no) at Week 24 (Part A) and Weeks 12 and 16 (Part B)

Part A

The reduction from baseline to Week 24 in the CLASI-A score will be calculated for each subject. The proportion of subjects who had ≥ 4 -point CLASI-A response at week 24, defined as a ≥ 4 -point reduction in the CLASI-A score from baseline at week 24, will be analyzed as described for binary endpoint analysis in [Section 6.1.1](#).

Part B

The reduction from baseline to Week 12 and 16 in the CLASI-A score will be calculated for each subject. The proportion of subjects who had ≥ 4 -point CLASI-A response at week 12 or week 16, defined as a ≥ 4 -point reduction in the CLASI-A score from baseline at week 12 or 16, will be analyzed separately for each time point as described for binary endpoint in [Section 6.1.2](#).

6.3.3. A 7 Point Reduction in CLASI-A Response (yes/no) at Week 24 (Part A) and Weeks 12 and 16 (Part B)

Part A

The reduction from baseline to Week 24 in the CLASI-A score will be calculated for each subject. The proportion of subjects who had ≥ 7 -point CLASI-A response at week 24, defined as a ≥ 7 -point reduction in the CLASI-A score from baseline at week 24, will be analyzed as described for binary endpoint analysis in [Section 6.1.1](#)

Part B

The reduction from baseline to Week 12 and 16 in the CLASI-A score will be calculated for each subject. The proportion of subjects who had ≥ 7 -point CLASI-A response at week 12 or week 16, defined as a ≥ 7 -point reduction in the CLASI-A score from baseline at week 12 or 16, will be analyzed separately for each time point as described for binary endpoint in [Section 6.1.2](#).

CONFIDENTIAL

The information contained herein may not be used, disclosed, or published without the written consent of Biogen MA Inc.

 Biogen	Statistical Analysis Plan 230LE201	<V 2.0>
--	---	----------------------

6.3.4. Percent Change in CLASI-A Score from Baseline at Week 12, 16 and 24 (Part A) and Week 12 (Part B)

The change from baseline to each post-baseline week in the CLASI-A score will be analyzed will be analyzed as described for continuous endpoint analysis in [Section 6.1.1](#) (Part A) and [Section 6.1.2](#) (Part B). Summary statistics for actual values and change from baseline will also be presented by week based on observed data.

6.3.5. Proportion of Subjects with an SLE Responder Index (SRI) Response of ≥ 4 at Week 24 (Part A Only)

SLE Responder Index (SRI) of ≥ 4 (SRI-4) at Week 24 is a categorical response variable (yes/no) incorporating the following criteria for achievement of responder status (i.e., all criteria must be met to achieve responder status):

- A reduction from baseline of ≥ 4 points in Systemic Lupus Erythematosus Disease Activity Index 2000 (SLEDAI-2K), and
- No new organ system affected, as defined by no new British Isles Lupus Activity Group (BILAG)-2004 grade A and no more than one new BILAG-2004 grade B, and
- No worsening from baseline in subject's lupus disease activity defined by <1 point increase in the Physician's Global Assessment (PGA) [visual analog scale (VAS)] (in the scale of 0-10) and
- No changes to protocol specified medications rules as described below (all criteria must be met):
 - No initiation or increase of SLE standard of care therapy or other disallowed concomitant therapy (see table 8 from latest protocol for protocol-prohibited list).
 - Concomitant corticosteroid dosage at Week 24 to be ≤ 10 mg/day.
 - Concomitant corticosteroid dosage at Week 24 to be \leq Day 1.
 - No increase in corticosteroid dose between weeks 17 and 24.

CONFIDENTIAL

The information contained herein may not be used, disclosed, or published without the written consent of Biogen MA Inc.

The proportion of subjects who had a composite response, as defined above, will be analyzed as described for binary endpoint analysis in [Section 6.1.1](#). Proportion of subjects who responded to each of the 4 criteria will also be reported.

